2 PURPOSE OF THE STUDY AND STUDY OBJECTIVES

2.1 Purpose of the Study

^{68}Ga -OPS202 PET/CT has been solely investigated in patients with NETs. Non-NETs expressing sstr2 may have a different level of receptors expression raising the question of a possible difference in terms of optimal uptake time. This phase II study aims to estimate firstly the percentage of female subjects with newly diagnosed breast cancer who have sstr2 positive lesions using ^{68}Ga -OPS202, secondly in those subjects with sstr2 positive tumours, the optimal PET acquisition time based on detected number of lesions and tumour to background ratio in subjects with sstr2 positive breast cancer. The study will also expand the evaluation of ^{68}Ga -OPS202 safety in patients with non-NETs expressing sstr2.

2.2 Study Objectives

The co-primary objectives of the study are:

- To evaluate the percentage of women with newly diagnosed breast cancer who have sstr2 positive lesions that are identified using ^{68}Ga -OPS202
- To define the optimal PET imaging time of ^{68}Ga -OPS202 at 0.5, 1.0 and 2 hours post injection, based on detected lesions in adult women with sstr2 positive newly diagnosed early or advanced breast cancer.

The secondary objectives of the study are as follows:

- To further define the optimal uptake time of ^{68}Ga -OPS202 based on quantitative SUV_{max} and other quality parameters
- To describe the safety and tolerability of ^{68}Ga -OPS202 in women with newly diagnosed (early or advanced) sstr2 positive breast cancer

The exploratory objectives of the study are as follows:

- To provide preliminary estimates of the sensitivity of ^{68}Ga -OPS202 PET/CT scan imaging, as well as SUV ratio (SUV_{max} lesion/ SUV_{mean} reference tissue) and signal-to-noise ratios (SNR)
- To assess the correlation in terms of number of avid lesions between ^{18}F -fluorodeoxyglucose (^{18}F -FDG)-PET and ^{68}Ga -OPS202
- To assess the correlation between ^{68}Ga -OPS202 tumour uptake with results from immunohistochemistry staining of sstr2.

2.3 Study Hypothesis

The uptake of ^{68}Ga -OPS202 does not vary according to PET acquisition time within a range of 1.5 hours in subjects with sstr2 positive newly diagnosed breast cancer, taking into account the ^{68}Ga decay.

3 STUDY DESIGN

3.1 General Design and Study Schema

This is a non-randomised phase II study, with an approximately 4-week duration for each subject and central review-blinded reader endpoint.

All subjects will receive a single dose of ^{68}Ga -OPS202 (IIP), consisting of a peptide mass up to 45 μg , with a radioactivity range of 150-200 MBq. ^{68}Ga -OPS202 is prepared up to 3 hours prior to administration by ^{68}Ga -radiolabelling of an OPS202 radiolabelling kit.

Three PET images will be acquired at 0.5, 1.0 and 2.0 hours post ^{68}Ga -OPS202 injection.

^{18}F -FDG-PET scan, which is part of routine clinical diagnosis, will be acquired at any time during the study period (including the Screening period), according to the investigator site's standards.

A single ceCT scan is required for the study. This can be acquired following either of the two PET scans (FDG-PET or ^{68}Ga -OPS202 post the 2-hour acquisition). Only one ceCT scan is required to minimise radiation dose. Low-dose CT scans will be acquired for the other PET scans when the ceCT is not obtained. For the ^{68}Ga -OPS202 PET scan a single low dose CT scan is preferred for the 0.5 and 1.0-hour post dosing acquisitions.

All images (^{68}Ga -OPS202 PET/CT scans, ^{18}F -FDG-PET/CT scan, and ceCT scan) will be sent to an imaging core laboratory (ICL) for central blinded reading. See Section 7 and the Imaging Review Charter (IRC) for further details.

All decisions regarding subjects' medical management will be made locally by the treating physicians (images read locally for this purpose). The ICL/central readers will only evaluate the images for the study endpoints and the information will not be provided to the sites on an individual subject basis.

The Screening Visit (Visit 1) will be performed within 14 days prior to the ^{68}Ga -OPS202 administration. At Screening, after obtaining written informed consent, the investigator will collect all the information required to confirm the subject eligibility including medical and surgical history, physical examination and vital signs, laboratory tests (haematology, blood chemistry and urinalysis) and tumour histopathology if available. Tumour biopsy, which is not a prerequisite for inclusion, is routinely performed for confirmation and staging of the disease, as well as classification according to hormone receptor status and human epidermal growth factor receptor 2 (HER2) status. For the study, the collection of an archived tumour sample (a block is preferred over paraffin embedded slides) is required for the evaluation of sstr2 expression by immunohistochemistry staining.

[figure not shown]
Subjects' eligibility will be re-checked by the investigator at Baseline/Day 1 (Visit 2) before administration of the IIP. If eligibility is re-confirmed, the subject will receive one injection of ^{68}Ga -OPS202 followed by whole body PET acquisition at 0.5, 1 and 2 hours after the injection of the IIP. A single ceCT scan will be performed according to the site standard procedure for chest, abdomen, pelvis and brain. This can be acquired after either of the two PET scans (^{18}F -FDG-PET or ^{68}Ga -OPS202 post the 2-hour acquisition). Low-dose CT scans will be acquired with PET scans when necessary for attenuation correction.

Subjects may be hospitalised overnight upon completion of the ^{68}Ga -OPS202 PET/CT scans at the discretion of the investigator. All subjects (either hospitalised or not) will attend a consultation on Day 2 for vital signs and laboratory tests. Also an ^{18}F -FDG-PET scan and ceCT scan will be arranged if not already acquired.

An End of Study Visit (Visit 3) will take place on Day 14 (± 3 days), during which the investigator will collect the safety information required by the study protocol (see Criteria of safety evaluation below). At the end of Visit 3, the subject's participation in the study will end. For any adverse event (AE) emerging or worsening during the study that persists beyond Visit 3, the investigator will monitor the subject until the AE is resolved or considered stabilised.

Study design scheme is presented in Figure 1.

Figure 1 Study Design

*A single contrast enhanced computed tomography (ceCT) scan is required for the study. This can be acquired after either of the two PET scans (^{18}F -FDG-PET or ^{68}Ga -OPS202 post the 2-hour acquisition). ^{18}F -FDG-PET scan, will be acquired at any time during the study period (including the Screening period), according to the investigator site's standards

#Women with readable ceCT scan and at least two ^{68}Ga -OPS202 PET scans that are readable

CT=computed tomography, h=hour, IIP=investigational imaging product, PET=positron emission tomography

Note: Approximately 54 subjects will be screened to receive IIP to identify 16 sstr2 positive evaluable subject scans.

3.2 Primary and Secondary Endpoints and Evaluations

The primary and secondary imaging endpoints will be read by third-party independent readers. Co-primary and secondary endpoints will be measured in the primary tumour and key organs consisting of liver, lymph nodes, bone, lungs and brain.

3.2.1 Primary Efficacy Endpoint and Evaluation

- Percentage of subjects with sufficiently avid lesion(s) to be identified as a sstr2 positive lesion. (Avid is defined by the blinded readers at one of the acquisition timepoints as an easily identifiable lesion radiologically, where there has been clear focal uptake of ^{68}Ga -OPS202 and 1.5-fold or greater uptake than the non-tumoural liver and lung parenchyma).
- Differences in the number of lesions detected by ^{68}Ga -OPS202 between the three PET acquisition timepoints (0.5, 1 and 2 hours), and reader interpretation of optimal image(s) in the primary breast lesions.

3.2.2 Secondary Endpoints and Evaluations

3.2.2.1 Key Secondary Endpoint

- Differences in the number of lesions detected by ^{68}Ga -OPS202 between the three PET acquisition timepoints (0.5, 1 and 2 hours), and reader interpretation of optimal image(s) in nodular and metastatic lesions. Significant uptake of ^{68}Ga -OPS202 for the evaluation

of a lesion is an avid lesion defined by the blinded readers at one of the acquisition timepoints as an easily identifiable lesion radiologically, where there has been clear focal uptake of ^{68}Ga -OPS202 and 1.5-fold or greater uptake than in the non-tumoural liver and lung parenchyma.

- The SUV_{mean} and SUV_{max} in the primary lesion between each of the three timepoints, measured in the most avid lesions (using the ^{68}Ga -OPS202 scans). This is assessed by the tumour-to-background ratio in the primary tumour and each of the major anatomic sites (liver, lymph nodes, bone, lungs and brain); the background consists of non-tumoural liver parenchyma or aortic blood where sufficient liver is not available. Identification of lesions to be used will be made by one of the two primary readers.

3.2.2.2 *Other Secondary Endpoints*

- Differences in relative lesion counts as a ratio of the number of lesions detected by ^{68}Ga -OPS202 at 0.5, 1 and 2 hours post dose respectively, compared to the number of lesions assessed by standard-of-truth (descriptive analyses). The standard-of-truth is the ^{18}F -FDG-PET/CT scan images acquired at any time during the study period (including the Screening period). This will be calculated by (number of lesions detected by ^{68}Ga -OPS202) / (number of lesions detected by ^{18}F -FDG-PET).
- Differences of absolute number of lesions between the three PET acquisition timepoints detected in each of the following anatomic sites:
 - Lymph nodes
 - Liver
 - Axial/appendicular skeleton
 - Lungs
 - Brain

The primary and appropriate secondary endpoints will also be evaluated on a MBq/kg of body weight.

The secondary endpoints will be summarised by each of the three PET acquisition timepoints (0.5, 1 and 2 hours).

3.2.3 *Exploratory Endpoints*

- Preliminary diagnostic sensitivity of ^{68}Ga -OPS202 imaging of breast cancer expressing sstr2 positive by both subject-based and lesion-based analysis compared to standard-of-truth
- SNR calculated from lesion-free volume of interest (VOI) in the liver: $\text{SUV}_{\text{mean}}/\text{SUV}_{\text{SD}}$ at the three PET acquisition timepoints
- Estimated correlation in terms of number of avid lesions between ^{68}Ga -OPS202 PET at the agreed “optimum timepoint” and ^{18}F -FDG-PET
- Estimated correlation between ^{68}Ga -OPS202 PET uptake and results of immunohistochemistry staining of sstr2 of the primary tumour.

For further details on efficacy endpoints, refer to Section 7 and the IRC.

3.2.4 *Safety Endpoints and Evaluations*

The investigator will report the occurrence of any AE throughout the study and vital signs (including blood pressure and heart rate) measurements at each visit: Screening Visit (Visit 1; Day -14 to -1), Visit 2 (Day 1), Visit 2 (Day 2) and End of Study/Early Withdrawal Visit

(Visit 3). Clinically significant abnormalities in laboratory tests (serum chemistry, haematology, and urinalysis) measurements will be reported at Screening Visit, Visit 2 (Day 2) and End of Study/Early Withdrawal Visit. Physical examination findings and body weight measurements will be reported at Screening Visit, Visit 2 (Day 1) and End of Study/Early Withdrawal Visit. The electrocardiogram (ECG) findings are to be recorded at the Screening Visit and the End of Study/Early Withdrawal Visit. Relevant medical history and concomitant medications/therapies will also be recorded throughout the study.

The following safety endpoints will be evaluated:

- Proportion of subjects experiencing at least one AE of any grade according to the National Cancer Institute-Common Terminology Criteria for Adverse Events (NCI-CTCAE) version 5.0, including any serious AEs including suspected unexpected serious adverse reactions (SUSARs); all AEs will be coded using the Medical Dictionary for Regulatory Activities (MedDRA) system organ class (SOC) and preferred term (PT) (as per most recent version)
- Proportion of subjects experiencing at least one AE of grade ≥ 3 according to NCI CTCAE.
- Clinically significant changes in physical examination, vital signs, ECG and laboratory findings, which will be recorded by the investigator as AEs.

3.3 Randomisation and Blinding

This is an open-label non-randomised study. However, the independent readers will evaluate ^{68}Ga -OPS202 PET/CT and ^{18}F -FDG-PET/CT images and will be blinded to the acquisition time of the PET scans and CT scans, investigator site and clinical status of the subject, including pathology, laboratory, medical history and physical exam findings.

Independent readers are specialised radiologists and/or nuclear medicine physicians who are experienced in reading PET/CT scans. To minimise inter- and intra-reader variability in results, the readers will be specifically trained for this protocol. Two readers will read 100% of all the images and third will adjudicate any differences. See the Imaging Review Charter (IRC).

3.4 Maintenance of Randomisation and Blinding

All blinding is handled by the ICL and described in the IRC.

3.5 Study Imaging Product and Dosage

The IIP is provided in a sterile two-vial radiolabelling kit constituted of freeze-dried powder containing 50 μg non-radiolabelled precursor OPS202 and excipients (Vial A) and the solvent for reconstitution (Vial B) to be used prior to radiolabelling.

The radiolabelling kit must be maintained between + 2 °C and + 8 °C until reconstitution.

Radiolabelling yields the IIP ^{68}Ga -OPS202 as a solution for injection, placed in a shielding secondary container. This shielding container will be labelled according to local requirements and identified with a radiolabelling batch number and the subject number. The volume to be administered to the subject is withdrawn from the IIP vial. This volume is determined to obtain the target radioactivity dose at the time of administration, taking into account the decay of ^{68}Ga . All subjects will receive a single dose of 150-200 MBq ^{68}Ga -OPS202 (IIP), as a slow i.v. bolus injected over 1 minute.

A more detailed description of preparation and administration procedures is given in Section 6.1.1.

The radiolabelling kit will be packaged and delivered in a sufficient quantity to the investigational sites with a delivery note including an acknowledgement of receipt.

The investigator's representative will receive:

- For each batch of radiolabelling kit that will be used during the study, a Certificate of Compliance and Certificate of Analysis, which reflects the product release statement,
- Material Safety Data Sheet,
- Delivery note including an Acknowledgement of Receipt (AoR), Packaging Order.

All the labels identifying the radiolabelling kits will be designed in accordance with all requirements of Good Manufacturing Practice (GMP) and applicable national laws in force in the countries. The label of the radiolabelling kit and the label of lead container will be translated into local languages.

The investigator, or designee, will only dispense IIP to subjects included in this study. Each subject will only be given the IIP carrying his/her number. The dispensing for each subject will be documented in the eCRF.

3.6 Study Duration

Subject participation in the study will include:

- Visit 1: a screening period up to 14 days prior to IIP administration
- Visit 2: a single i.v. injection of between 150 MBq to 200 MBq of ⁶⁸Ga OPS202 on Day 1 followed by PET acquisition at 0.5, 1 and 2 hours ±10 minutes post dosing,
- Visit 3: a follow-up visit at Day 14 (±3 days) for evaluation of safety.
Within the study an ¹⁸F-FDG-PET scan and also a ceCT scan must also be acquired.

The subject's participation in the study will be considered to have ended at the time of the last visit (Visit 3, at Day 14 ±3 days).

The overall duration of the study will be approximately 4 weeks for each subject. The study will be considered to have started when the first subject has provided signed informed consent.

The study will be considered to have ended after the last subject has completed the last follow up period in the study.

3.7 Stopping Rules and Discontinuation Criteria

During the conduct of the study, SAEs will be reviewed (see Section 8.1.3) as they are reported from the study centres to identify safety concerns. A specific site or a given cohort can be discontinued or the entire study may be terminated at any time if the sponsor judges it necessary for any reason. In that case, all scheduled procedures and assessments for subjects who are still in the study will be performed. Some possible reasons for the closure of a study site may include:

- failure of the Investigator staff to comply with the protocol or with the GCP guidelines
- safety concerns
- inadequate subject recruitment.

The study may be terminated by the sponsor at any time.

A subject may discontinue participation in the study at any time for any reason (e.g. withdrawal of consent, AE). The investigator and/or sponsor can withdraw a subject from the study at any time for any reason (e.g. protocol deviation as defined in Section 13.1.2, noncompliance with the protocol conditions or AE). All cases of discontinuation will be discussed between the investigator and the sponsor.

Futility Stopping Rule

If less than three sstr2 positive evaluable subject scans out of 30 consecutive subjects screened with ⁶⁸Ga-OPS202 PET/CT, or less than 8 out of 50, the study will be stopped.

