Considering the estimated prevalence of sstr2 overexpression in breast cancer, it is anticipated that a total of approximately 54 subjects will be enrolled in the study for ^{68}Ga -OPS202 PET/CT imaging, to obtain 16 sstr2 positive breast cancer (BC) evaluable subjects. However, when the ICL identifies 16 sstr2 positive evaluable subject scans, with a minimum of two subjects with advanced disease, the study will be complete.

Futility Stopping Rules

If less than three sstr2 positive evaluable subject scans out of 30 consecutive subjects screened with ^{68}Ga -OPS202 PET/CT, or less than 8 out of 50, the study will be stopped.

The Sponsor may consider stopping subject recruitment and revisit the study design with possible termination of the study when justified.

Diagnosis and criteria for inclusion:

Following a screening period of up to 2 weeks, eligible subjects will be enrolled in the study if they meet all the following inclusion criteria, and none of the following exclusion criteria:

Inclusion criteria:

1. Women aged 18 years or older
2. Subjects with newly diagnosed (early or advanced) breast cancer
3. Eastern Cooperative Oncology Group (ECOG) performance status ≤ 2
4. Adequate bone marrow, liver and renal function, with:
 - Calculated glomerular filtration rate (GFR): ≥ 45 mL/min
 - Albumin: > 30 g/L
 - Alanine aminotransferase (ALT), aspartate aminotransferase (AST), alkaline phosphatase (AP): ≤ 5 times upper limit of normal (ULN)
 - Bilirubin: $\leq 3 \times \text{ULN}$ (3×1.1 mg/dL)
 - Leukocytes: $\geq 3 \times 10^9/\text{L}$, and neutrophils: $\geq 1 \times 10^9/\text{L}$
 - Erythrocytes: $\geq 3.5 \times 10^{12}/\text{L}$
 - Platelets: $\geq 90 \times 10^9/\text{L}$
5. Signed written informed consent prior to any study-related procedures.

Exclusion criteria:

1. Subjects with resected primary tumour
2. Subjects with confirmed ductal carcinoma in situ
3. Men with breast cancer

4. Presence of an active infection at screening or history of a serious infection within the previous 6 weeks prior to the first ^{68}Ga -OPS202 administration that might interfere with the PET and/or CT analysis
5. Subjects who have received any therapy for breast cancer
6. Prior or planned administration of a radiopharmaceutical within 8 half-lives of the radionuclide
7. Clinically relevant trauma within 2 weeks prior to first ^{68}Ga -OPS202 administration
8. Any condition that precludes the proper performance of PET and/or CT scan:

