11.2 Sample Size Determination

It is anticipated that a total of approximately 54 subjects will be enrolled in the study for ⁶⁸Ga-OPS202 PET/CT imaging, to obtain around 16 sstr2 positive BC evaluable subjects. Considering the estimated prevalence of sstr2 overexpression in breast cancer, the overall number of subjects to be administered ⁶⁸Ga-OPS202 in the study will be over 50. However, when the ICL identifies 16 sstr2 positive evaluable subjects, with a minimum of two subjects with advanced disease, the study will be complete.

This estimation of 16 sstr2 positive BC evaluable subjects is considered appropriate for a descriptive analysis and it is not based on a formal statistical sample size calculation. In the event that a subject misses an imaging exam and/or measurement relevant to the primary and key secondary endpoints, an additional subject will be recruited as a replacement to ensure an adequate sample size in the sstr2 positive BC evaluable set.

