11.6 Interim Analyses

No interim analysis will be performed.

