3.2.13 Interim analysis

No interim analysis will be performed. One final analysis will be performed at the end of the study, after database lock.

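### Must the futility rule say whether its 30 and 50 are the first subjects imaged or any run of that length?

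*Protocol*

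**What the plan says.** The rule stands in three places with the same wording: the Protocol synopsis, Protocol 3.7 and SAP 1.2.2. The first limit is "If less than three sstr2 positive evaluable subject scans out of 30 consecutive subjects screened with" the imaging product. The second follows at once: "or less than 8 out of 50, the study will be stopped". The word *consecutive* is attached to the 30 and is not repeated for the 50.

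The synopsis and SAP 1.2.2 add a discretionary power: "The Sponsor may consider stopping subject recruitment and revisit the study design with possible termination of the study when justified". Protocol 3.7 also lets the sponsor end the study at any time.

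On size, Protocol 11.2 says "It is anticipated that a total of approximately 54 subjects will be enrolled in the study for" imaging, to obtain around 16 positive evaluable subjects. It continues "Considering the estimated prevalence of sstr2 overexpression in breast cancer" and concludes that the number given the product "in the study will be over 50". The same section says that 16 does not come from a formal sample size calculation. The study is complete at 16 positive evaluable subjects, of whom at least two must have advanced disease.

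Protocol 11.6 states "No interim analysis will be performed", and SAP 3.2.13 states "No interim analysis will be performed. One final analysis will be performed at the end of the study, after database lock".

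**The concern.** A mandatory stopping rule should give the same answer to anyone who holds the same data. Three readings fit this text:

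- **A**: the first 30 and the first 50 subjects imaged.
- **B**: any 30 consecutive subjects, and the first 50.
- **C**: any 30 and any 50 consecutive subjects.

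They can disagree. Suppose there are 5 positives in the first 30, 9 in the first 50, and 2 among subjects 51 to 80. Reading A continues, since 5 is at least 3 and 9 is at least 8. Readings B and C stop by subject 80, because subjects 51 to 80 hold fewer than 3.

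No interim analysis is planned, so no other section says when the counts are made. Protocol 11.2 refers to a prevalence without restating its value and names no maximum enrolment. It could therefore seem that the number of women who might be imaged depends on an unstated reading, and that a later reader could not tell a stop required by the rule from a discretionary one.

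**Working it through.** **Inputs.** Limits: fewer than 3 of 30 and fewer than 8 of 50 (Protocol 3.7). Completion: 16 positive evaluable subjects, two of them advanced (Protocol 11.2). Planned number: about 54. The documents give no yield as a number in the sample-size or stopping sections, so every rate below other than 16/54 is an assumption.

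**The plan's own figure.** Expected number imaged = 16 / yield. A yield of 0.30 gives 16/0.30 = 53.3, which rounds up to 54. Working back, 16/54 = 29.6%. This is a yield of *evaluable* positives per subject enrolled. It is not a prevalence, because evaluability also needs two usable timepoints, an FDG-PET scan and a contrast-enhanced CT.

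**Reading A, exact binomial.** With X the positives in the first 30 and Y those in the next 20,

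P(stop) = P(X ≤ 2) + Σ P(X = k) · P(Y ≤ 7 − k), for k = 3 to 7.

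At 16/54 this is 0.0024 + 0.0073 = 0.0097.

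**All three readings.** B and C were simulated with 400,000 studies per rate. The counts were updated as each subject was added, the study was complete at the 16th positive, and the advanced-disease condition was left out. Chance of a futility stop:

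| Yield | A | B | C |
|---|---|---|---|
| 29.6% (implied) | 1.0% | 2.7% | 4.1% |
| 25% (assumed) | 4.9% | 10.9% | 16.6% |
| 20% (assumed) | 19.8% | 35.9% | 48.2% |
| 16% (assumed) | 44.9% | 68.1% | 79.5% |

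At the implied yield, A and C differ by 4.1 − 1.0 = 3.1 percentage points. The illustration above needs a block of 30 with fewer than 3 positives. For any one block at 29.6% that has probability 0.24%.

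**How much room the planned size leaves.** Among 54 subjects there are 54 − 50 + 1 = 5 runs of 50, all nearly the same as the first 50. There are 54 − 30 + 1 = 25 runs of 30. At the planned size, then, the reading of the 50 hardly matters, and the reading of the 30 matters mainly when the yield is low.

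**Does any reading cap enrolment?** If 16 positives were enough, reading C would force completion or a stop by subject 100, since two successive runs of 50 must each hold at least 8. But 16 positives are not enough. A study with 16 positives and fewer than two advanced subjects carries on under every reading as long as positives keep arriving. The chance of imaging more than 100 at 29.6%, by the assumed share of positives that are advanced, is:

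| Advanced share (assumed) | A | B | C |
|---|---|---|---|
| 10% | about 20% | about 19% | about 18% |
| 20% | 1.6% | 1.6% | 1.3% |
| 30% | about 0.1% | about 0.1% | about 0.1% |

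The share of advanced disease drives enrolment. The reading of the futility rule barely moves it.

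**The case for a change.** The best case for a change is that the rule is mandatory, the ambiguity appears in all three places, and the gap between readings is widest at yields of 16 to 25%, which is where a futility rule has to work. At 20%, going from about one study in five stopped to nearly one in two is not trivial. One added phrase for each limit would settle it and leave both limits untouched.

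The ambiguity and those probabilities stand. The rest is weaker:

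- The ordinary reading is available and workable. The imaging core laboratory already keeps a running count of positives from the first subject, because the study completes on that count. Comparing it with 3 at the 30th subject and 8 at the 50th needs no interim analysis. *Consecutive* then means that no subject is left out of the count.
- Choosing among the readings is a trade-off. Any-run counting stops more low-yield studies, and it also stops a few more at the planned yield. Neither choice is an error.
- The claim that one reading caps enrolment and another does not fails on the two-advanced condition.
- It cannot be asserted that the plan gives no prevalence, because part of the Protocol's background text is not in the copy reviewed. All that can be said is that Protocol 11.2 and SAP 1.3.4 do not restate it.
- Giving 54 with a percentile range is a preference in a study whose size is openly not calculated.

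**Conclusion.** The wording leaves a gap, but it is one that the study team can fill sensibly, and no change to the plan is called for. The limits of 3 of 30 and 8 of 50 are lenient minimum yields (10% and 16%) below the planned 29.6%. At that planned yield the choice of reading moves the chance of stopping by about 3 percentage points. The larger differences, such as 20% against 48%, rest on an assumed yield of 20% and leave out the advanced-disease condition. Enrolment has no cap under any reading.

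The consequences are also limited. The rule governs when recruitment ends in a descriptive study with no significance test, and the sponsor may stop at any time in any case. SAP 3.2.1 and SAP 5 record that the study was ended prematurely with limited data, so rewording could not alter a decision or a result. Neither section links that decision to the futility rule. If the rule was in fact used, the reading applied and the counts at the stop belong in the clinical study report (Protocol 17.2), which is a matter of reporting.
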